**g) Procedures Involved in the Human Research\***

All study procedures are done solely for the purposes of research.

***Study design***

This will be a randomized, placebo controlled, double-blind study investigating the effects of STIOLTOTTM RESPIMAT® on the mechanisms of exercise intolerance in COPD patients. The study is a crossover, within-patients, design comparing the effect STIOLTOTTM RESPIMAT® to placebo on dynamic hyperinflation, performance fatigue (PF), activation fatigue (AF), and muscle fatigue (MF) during and after constant power exercise to intolerance. Twenty-one patients with moderate to very severe disease will be recruited into this study.

Initially pulmonary function and cardiopulmonary exercise variables will be used to characterize recruited patients. Subsequently, constant power exercise tests (calculated from the initial incremental exercise test to bring the patient to intolerance in approx. 6 min) will be used to characterize the components of performance fatigue, ventilation, dynamic hyperinflation, skeletal muscle oxygenation, and accessory respiratory muscle activity. Patients will perform two

PROTOCOL TITLE: A randomized, crossover, placebo controlled, double-blind phase IV trial of the effect of on STIOLTO™ RESPIMAT® on central and peripheral components of fatigue during exercise in chronic obstructive pulmonary disease  
Revised: November 13, 2015

tests, each to the limit of tolerance, with prior STIOLTO™ RESPIMAT® bronchodilator and placebo. An independent statistician will randomize the order of these two tests, and both patients and investigators blinded to the condition. A pharmacist, who will otherwise not participate in the study, will facilitate drug administration. Unblinding information will be kept in sealed envelopes by the pharmacist in case of (S)AE.

A third constant power exercise test will be performed with the treatment that resulted in the longer endurance time. In this test the components of performance fatigue and dynamic hyperinflation will be measured at the duration at which the patient reached intolerance in the alternative treatment trial (i.e. isotime measurement). This will allow comparisons of PF, AF, and MF and their associations with ventilation, dynamic hyperinflation, skeletal muscle oxygenation, and accessory respiratory muscle activity, between STIOLTO™ RESPIMAT® and placebo at during and following exercise to intolerance and at isotime.

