Visits 3-5: Constant power exercise and fatigue tests. Visits 3-5 will each include spirometry, an exercise test (constant power exercise), and measurement of activation and muscle fatigue, dynamic hyperinflation, ventilation and gas exchange, accessory respiratory muscle activation, and leg muscle deoxygenation. The condition (active drug vs placebo) of visits 3 and 4 will be randomized and each test will be continued to the limit of tolerance. Visit 5 will be an 'isotime' test, in which the patient is stopped at the tolerable duration of the shorter test, using the condition that resulted in the longer duration. Visits 3-5 will be preceded by a 14-day washout period and 7 days using once-daily STIOLTOTTM RESPIMAT® bronchodilator treatment or placebo, with the condition blinded to the patient and investigators. Subjects will take their daily dose of the study medication 90 minutes before undergoing spirometry and constant work rate testing.

Fatigue measurements (particularly AF, and MF) are technically challenging to make, and sometimes a repeat visit is required to secure robust measurements. This occurred in about 15% of visits in our previous study (LA BioMed protocol 30044-01); typically repeated measurements are needed at visit 2 where the patient is initially introduced to the requirement to make a 5-second maximal effort to measure fatigue. Should a repeated visit be necessary, the patient will be continued in the study phase i.e. taking no drug (baseline, visit 2), or taking active drug or placebo (visit 3, 4 or 5). They will be recalled within approximately 1 week for re-testing. On completion of the repeat the subject will then be advanced to the next phase of the study (crossover or isotime).

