### ***Procedures***

An assessment schedule for the procedures in the study is shown in Table 1.

*Pulmonary function*: Visit 1 will include spirometry, lung volume by body plethysmography, and single-breath carbon monoxide diffusing capacity tests. Each will be made according to ATS/ERS guidelines, at least 10 min after 200 µg of albuterol (Millar et al., 2005). Visits 2-5 will include spirometry prior to each exercise test.

*Resting ECG*: Visit 1 will include a resting 12 lead ECG to determine a normal electrocardiogram prior to any exercise testing.

*Medical history and questionnaires*: During visit 1 a medical history will be collected, including respiratory and heart history, smoking history, and medication history. Patients will also complete the St. George's Respiratory

PROTOCOL TITLE: A randomized, crossover, placebo controlled, double-blind phase IV trial of the effect of on STIOLTOT™ RESPIMAT® on central and peripheral components of fatigue during exercise in chronic obstructive pulmonary disease  
 Revised: November 13, 2015

Questionnaire (SGRQ) and the COPD Assessment Tool (CAT) to assess COPD symptoms.

**Table 1.** Assessment Schedule

Study phase	Consent	Screening PFT	Baseline & Randomization	Fatigue test 1	Fatigue test 2	Isotime test
Visit number	-	1	2	3	4	5
Study days	up to -17	-14	0	7	28	49
Inclusion / Exclusion criteria	x	x				
Relevant History, Physical Exam		x				
Height & Weight		x	x	x	x	x
Spirometry		x	x	x	x	x
Lung Volumes		x	x	x	x	x
DL CO		x				
Resting ECG		x				
NIRS Oxidative Capacity Test		x				
CPET & ECG (Incremental)			x			
CPET & ECG (CWR)			x	x	x	x
EMG (Accessory & Leg muscles)			x	x	x	x
Isokinetic Test – Baseline Calibration			x	x	x	x
Isokinetic Test - Fatigue			x	x	x	x
Exercise Leg NIRS			x	x	x	x
Ventilation & Gas Exchange			x	x	x	x
Dynamic Hyperinflation			x	x	x	x
Comments				As required		

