The constant power test will be repeated on at least 4 occasions. The initial constant power test will be made at least 2 hours after the incremental test and will be used to identify the ~6 min endurance time in untreated conditions (visit 2). If the endurance time is not ~6 min (in the range 4-10 minutes), then an additional visit (visit 2a) will be made to identify required power output. After this, two constant power tests will be performed to intolerance with either STIOLTOT™ RESPIMAT® or placebo (visits 3 and 4). An additional, third constant power test will be performed using the treatment condition that resulted in the longest endurance time (visit 5). For this test the isokinetic measurements will be made at a time when the shorter of the two treatment tests ended,

PROTOCOL TITLE: A randomized, crossover, placebo controlled, double-blind phase IV trial of the effect of on STIOLTOT™ RESPIMAT® on central and peripheral components of fatigue during exercise in chronic obstructive pulmonary disease  
Revised: November 13, 2015

providing isotime assessment. The condition (active drug vs placebo) of visits 3-5 will remain blinded to the participants and the experimenters until the end of the study. At the limit of tolerance and every 1 minute during recovery an isokinetic power test will be performed (described below).

*Isokinetic power tests (baseline and fatigue):* Patients will be familiarized with the maximal isokinetic cycling task at visit 2. Initially patients will be oriented to the cycle ergometer and optimal seat height will be determined. Following this, isokinetic ergometry tests will be performed at baseline, at the limit of tolerance, and in recovery during visits 2 (incremental exercise) and 3-5 (constant work rate tests).

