### ***Measurements***

*Ventilation, gas exchange, heart rate, and perceived exertion during exercise:*

During incremental and CWR exercise, patients will breathe through a mouthpiece for breath-by-breath pulmonary gas exchange and ventilation measurement (Vmax Encore, CareFusion USA). Heart rate, arterial oxygen

PROTOCOL TITLE: A randomized, crossover, placebo controlled, double-blind phase IV trial of the effect of on STIOLTOT™ RESPIMAT® on central and peripheral components of fatigue during exercise in chronic obstructive pulmonary disease

Revised: November 13, 2015

saturation, and transcutaneous CO2 partial pressure will also be measured.

[figure not shown]
Patients will be asked to rate their perceived exertion (“rate your leg fatigue” and “rate your difficulty of breathing”) every 2 minutes during exercise and recovery. All methods are well established in our lab. From these measurements the following variables will be determined in the incremental test: Peak oxygen uptake, lactate threshold (LT), ventilatory equivalent for CO2 at LT as an index of ventilatory efficiency, peak ventilation (also expressed relative to maximum voluntary ventilation calculated from pulmonary function tests).

*Tissue oxygenation:* Tissue oxygenation dynamics [(oxygenated hemoglobin and myoglobin) / (total heme-chromophor concentration)] will be measured in the quadriceps using spatially-resolved near-infrared spectroscopy (NIRO200, Hamamatsu; as previously described in our laboratories; Bowen et al., 2012). Kinetic modeling of deoxygenation response dynamics will be made by non-linear least squares fitting procedures to determine the association between tissue oxygenation and fatigue characteristics.

*Dynamic hyperinflation (DH):* DH will be evaluated from inspiratory capacity (IC) measurements at rest, every 2 min during exercise, and at end-exercise and during recovery (Somfay et al., 2001) immediately prior to the AF and MF measurement. This reproducible method allows dynamic changes in the operational lung volume to be determined.

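### The STIOLTO-versus-placebo comparison of dynamic hyperinflation at isotime should be read from the randomised Visits 3 and 4, not from Visit 5, which is always the last test

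*Combined protocol and SAP*

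**What the plan says.** All references are to the combined protocol and SAP.

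- **Source of isotime DH.** Section 8 g), Study design, describes a third constant power test on whichever treatment the patient tolerated for longer, and states: "In this test the components of performance fatigue and dynamic hyperinflation will be measured at the duration at which the patient reached intolerance" on the alternative treatment. The same section describes the crossover as comparing STIOLTO with placebo on DH as well as on performance fatigue (PF), AF and MF.
- **What is randomised.** Visit schedule: "The condition (active drug vs placebo) of visits 3 and 4 will be randomized and each test will be continued to the limit of tolerance". The final test, Visit 5, uses the condition with the longer duration and is one "in which the patient is stopped at the tolerable duration of the shorter test". It can only follow the other two.
- **Timing.** Table 1 gives "Study days up to -17 -14 0 7 28 49"; the last three are Visits 3, 4 and 5.
- **What each test records.** Measurements: "DH will be evaluated from inspiratory capacity (IC) measurements at rest, every 2 min during exercise, and at end-exercise and during recovery". Ventilation and gas exchange are breath by breath, and NIRS runs during exercise. Exertion is rated every 2 min, with no end-exercise rating scheduled. The maximal isokinetic effort that yields PF, AF and MF is made only at limitation or isotime, and in recovery.
- **Analysis.** Section 8 i), Analysis Plan, gives paired t-tests for isotime AF and MF with no period term, and linear regression of AF and MF on DH and deoxygenation at isotime, end-exercise and recovery. It does not say which visits supply a drug-placebo comparison of DH at isotime.

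**The concern.** The argument of the trial is that STIOLTO lowers DH and that this releases muscle activation. Showing lower DH at the same exercise time is the first link. If that contrast comes from Visit 5, a later test is always set against an earlier one, whatever the randomised sequence. Practice, habituation and change in the disease over the study then cannot cancel.

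For PF, AF and MF this is unavoidable, because the maximal effort is made only once the test is stopped. For DH, ventilation and oxygenation it is avoidable. The longer of Visits 3 and 4 passes through isotime on the other treatment, and the shorter one ends there, so the contrast already exists inside the randomised pair.

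Visit 5 also gives an isotime value only on the longer-lasting treatment. A patient who lasts longer on placebo has a placebo Visit 5 and no STIOLTO isotime value from it.

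**Working it through.** The plan states no figure for DH. Its only design calculation (power 0.95 for AF and MF, n = 21) is not affected, so there is nothing to reproduce for this point.

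**1. Order.** From Table 1, Visits 3, 4 and 5 are on days 7, 28 and 49. The lag from comparator to Visit 5 is 49 − 28 = 21 days (one visit step) or 49 − 7 = 42 days (two steps). If Visits 3 and 4 are equally often the shorter test, the mean is (21 + 42)/2 = 31.5 days, or 1.5 steps.

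**2. Bias from a linear drift of d per visit.**
- Visit 5 minus its comparator: d or 2d, mean 1.5d. If practice lengthens endurance, Visit 3 is the shorter test more often and the mean moves towards 2d.
- In STIOLTO-minus-placebo terms the sign reverses when placebo lasted longer. If a proportion p last longer on STIOLTO, the mean is 1.5d(2p − 1): 1.5d at p = 1, and 0.9d at an assumed p = 0.8.
- Visit 3 versus Visit 4: +d in one sequence and −d in the other, so 0 with balanced sequences. With an 11:10 split of 21 patients it is d × (11 − 10)/21 = 0.05d, which a period term removes.

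**3. What a drift could do (illustration only).** The documents give no drift. Assume g standard deviations per visit, p = 1, no true drug effect, n = 21, and a two-sided paired t-test at 0.05. Borrow r = 0.80, which the plan gives for the fatigue measures and not for IC. The standardised bias is 1.5g/√(2(1 − 0.80)) = 1.5g/0.632.

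| g | Standardised bias | False-positive rate |
|---|---|---|
| 0.05 | 0.119 | 0.08 |
| 0.1 | 0.237 | 0.18 |
| 0.2 | 0.474 | 0.54 |
| 0.3 | 0.712 | 0.87 |

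**4. Are the data at Visits 3 and 4 close enough to isotime?** In the shorter test, isotime is end-exercise, where IC is measured. In the longer test, IC readings lie 2 min apart, or closer where the end-exercise reading comes next. Isotime is therefore bracketed by readings at most 2 min apart, and one of them is within 1.0 min. With isotime assumed uniform over 4–10 min, the mean distance to the nearest reading is 0.5 min if the longer test runs at least 1 min further. It is 0.375 min (maximum 0.5) if it runs 0.5 min further. Ventilation and NIRS can be read at isotime itself.

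**5. Would Visit 5 against the earlier test on the same treatment isolate drift?** No, because the earlier test was selected as the longer one. Let ρ be the within-patient correlation between occasion-level IC and endurance, and δ the drug effect on endurance in occasion SDs. With zero drift, the selected test has an expected excess of ρ√2·φ(δ/√2), where φ is the standard normal density. This is 0.564ρ at δ = 0 and 0.208ρ at δ = 2. For assumed ρ of 0.3 to 0.5 it runs from 0.3 × 0.208 = 0.06 to 0.5 × 0.564 = 0.28 occasion SD.

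**The case against.** **The plan needs Visit 5 DH for association, not for a treatment contrast.** The secondary objective and the Analysis Plan relate DH to PF, AF and MF by regression, no isotime test of DH is written, and IC is taken immediately before the fatigue effort. For that use, IC must come from the same test as AF and MF. This stands, and Visit 5 IC should be kept for it. It does not settle the matter: Study design also sets out a STIOLTO-versus-placebo comparison of DH, and Visit 5 is the only isotime source it names.

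**Visits 3 and 4 are not excluded.** A reader might infer that the protocol discards their DH data. It does not: DH is scheduled at all three visits and nothing forbids using it. What is missing is an analysis rule.

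**Drift may be small.** Patients do a familiarisation constant work rate test with IC manoeuvres at Visit 2. That should reduce early practice effects, but it does not remove later ones or a change in the disease.

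**Visit 5 measures IC exactly at isotime.** True. Reading it from the longer of Visits 3 and 4 needs interpolation, which is exact only if IC changes linearly between readings.

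**Blinding.** A reader might infer that Visit 5 is unblinded. Treatment identity stays blinded at Visits 3 to 5; staff know only that Visit 5 repeats the longer-lasting condition.

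**Conclusion.** The point holds for DH, ventilation, oxygenation and perceived exertion compared between STIOLTO and placebo at isotime. Taken from Visit 5, that contrast is confounded with visit order by one or two visit steps (21 or 42 days), always in the same direction in time. Taken from Visits 3 and 4, it is protected by randomisation and exists for every patient who completes both, whichever treatment lasted longer and even if Visit 5 is missed.

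The size of the bias is unknown. The 1.5d average assumes linear drift and that order is unrelated to which test is shorter; the false-positive rates are illustrations. No bias in millilitres can be derived from the documents.

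Two stronger readings are not supported. One is that Visit 5 is unnecessary: isotime PF, AF and MF cannot be obtained without it. The other is that comparing Visit 5 with the earlier same-treatment test would measure the order drift behind the AF and MF results: that comparison mixes drift with regression to the mean.

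**What to change.** Add to the Analysis Plan:

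- The STIOLTO-versus-placebo comparison of DH, ventilation, oxygenation and perceived exertion at isotime uses Visits 3 and 4. It is analysed as STIOLTO minus placebo, with a period term, in every patient who completes both.
- The end-exercise value of the shorter test is set against the other test at the same time. Ventilation and NIRS are read at isotime, and IC is interpolated between the adjacent readings.
- Perceived exertion is compared at the last common 2-min rating, since no end-exercise rating is scheduled. That rating can fall almost 2 min before isotime.
- Visit 5 IC is paired with Visit 5 AF and MF in the association analysis, and used for the isotime DH contrast only as a sensitivity analysis.
- If Visit 5 is compared with the earlier test on the same treatment, the report states that the result mixes drift with regression to the mean.
- The text states that treatment identity remains blinded at Visit 5, although staff know that it repeats the longer-lasting condition.

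No visit, procedure or sample size changes. The small downside is that IC is interpolated over at most about 2 min instead of being measured exactly at isotime.

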#### ***Visit schedule***

Written informed consent will be administered in the study center. Consenting subjects will discontinue long-acting bronchodilators for the entire duration of the study. All subjects will receive albuterol (either alone, or as a combination therapy; see below for details) to be taken as needed (prn) for the duration of the study. For those subjects prescribed long-acting antimuscarinic therapy at study entry, during the three washout periods of the protocol subject's therapy shall consist of combination albuterol and ipratropium (Combivent) prn. Patients taking a combination long-acting beta agonist and inhaled corticosteroid therapy (LABA+ICS) at study entry will be transitioned to ICS monotherapy for the duration of the study. The study drug (STIOLTO™ RESPIMAT® or placebo) will be administered daily during three 1-week periods during the protocol. Each time, the study drug will be taken for one week before testing is performed. The study timeline is shown in Figure 1. The study will require a total 5 visits by each patient for pulmonary function and exercise tests.

Visit 1: Baseline pulmonary function test. Visit 1 will occur after consent and will include full pulmonary function assessment including pre- and post-bronchodilator spirometry, resting ECG, and muscle NIRS test.

Visit 2: Baseline cardiopulmonary exercise tests. Visit 2 will include spirometry, an incremental exercise test, and a constant power exercise test on a cycle ergometer. This testing day will be preceded by a 14-day washout of all long acting bronchodilators, and an overnight washout of short-acting albuterol. COPD questionnaires will be completed.

PROTOCOL TITLE: A randomized, crossover, placebo controlled, double-blind phase IV trial of the effect of on STIOLTOTTM RESPIMAT® on central and peripheral components of fatigue during exercise in chronic obstructive pulmonary disease  
Revised: November 13, 2015

Visits 3-5: Constant power exercise and fatigue tests. Visits 3-5 will each include spirometry, an exercise test (constant power exercise), and measurement of activation and muscle fatigue, dynamic hyperinflation, ventilation and gas exchange, accessory respiratory muscle activation, and leg muscle deoxygenation. The condition (active drug vs placebo) of visits 3 and 4 will be randomized and each test will be continued to the limit of tolerance. Visit 5 will be an 'isotime' test, in which the patient is stopped at the tolerable duration of the shorter test, using the condition that resulted in the longer duration. Visits 3-5 will be preceded by a 14-day washout period and 7 days using once-daily STIOLTOTTM RESPIMAT® bronchodilator treatment or placebo, with the condition blinded to the patient and investigators. Subjects will take their daily dose of the study medication 90 minutes before undergoing spirometry and constant work rate testing.

Fatigue measurements (particularly AF, and MF) are technically challenging to make, and sometimes a repeat visit is required to secure robust measurements. This occurred in about 15% of visits in our previous study (LA BioMed protocol 30044-01); typically repeated measurements are needed at visit 2 where the patient is initially introduced to the requirement to make a 5-second maximal effort to measure fatigue. Should a repeated visit be necessary, the patient will be continued in the study phase i.e. taking no drug (baseline, visit 2), or taking active drug or placebo (visit 3, 4 or 5). They will be recalled within approximately 1 week for re-testing. On completion of the repeat the subject will then be advanced to the next phase of the study (crossover or isotime).

